## 5 GENERAL INFORMATION FOR THE ANALYSES

	
e-CIG VS. IQOS Statistical Analysis Plan Version 2.0
	Doc code: BIOSTAT.SAP.02
		Pag. 10 of 115

According to the study protocol the statistical analysis will be descriptive in nature.

All the data will be described using standard descriptive statistics, i.e. n, missing, mean, standard deviation, (25th, 50th, 75th) percentiles for numerical variables. As for the categorical variables, frequency tables with count and percentage will be used. In the core of the Statistical Report, the continuous variables will be presented as mean values  $\pm$  standard deviation (SD) or median value and interquartile range [IQR], and categorical variables as numbers and percentages. The descriptive analyses will be presented by group. As indicated in the study protocol, for the primary endpoint, the quit rate at 3 months in the experimental study group will be calculated with a non-inferiority threshold of 15%. The quit rates will be evaluated on an intention-to-treat basis: subjects known to have failed will be considered as treatment failures in the primary analysis along with subjects lost to follow-up.

All the analyses will be performed using SAS® Vers. 9.4.

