## 3 SAMPLE SIZE

	e-CIG VS. IQOS Statistical Analysis Plan Version 2.0	Doc code: BIOSTAT.SAP.02
		Pag. 9 of 115

Sample size determination (better detailed in the study protocol) for no-inferiority testing is based on the assumptions that:

- 1) expected quit rates based on most recent EC literature is about 20-25% and
- 2) that differences in quit rates between products under investigation should not exceed 10-15% (as per non-inferiority definition).

For sample size definition, Farrington-Manning Score Test for Proportion Difference was used, assuming:

- asymptotic normal distribution, upper one-tailed
- alpha 0.05
- nominal power 0.80

Thus:

- Null Proportion Diff. -0.15
- Ref Proportion 0.25
- N per group: 104

According to these hypotheses the required number of participants per study arm was 104. Hence 220 participants, 110 per group, had to be included.

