# 7 STATISTICAL ANALYSES OF THE EFFICACY ENDPOINTS

The analyses of the primary and secondary endpoints will be carried out of both the ITT and PP populations. Moreover, as for the Step Test and the Quality of Life (i.e. EQ-5D), a further analysis in the subpopulation of the "Continuous Quitter" will be presented.

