### **7.2.1 Smoking reduction derived from the use of HnB and EC**

The smoking reduction derived from the use of HnB and EC, will be computed at each visit. The analysis will be presented considering both the definition of “Reducer” included in the study protocol and the so called “Russell Standard” (clinical) for outcome assessment in clinical trials of smoking cessation treatments.

As for the protocol definition, a subject will be classified as “Reducer” if at least a 50% reduction in the number of conventional cigarette/day at each visit will be observed. The results will be summarized as frequency table. The comparison between the two groups will be performed at each visit with the chi-square test. The results will be included in Table E.2a (Appendix 2).

As for the Russell Standard analysis, due to the fact that the study endpoint was a 12 weeks, a small deviation was adopted. In fact, the timepoint considered in the Russell Standard is 52 week. In our case, the 12 week and the 24 week (i.e. the Follow-up observation) will be considered for the analysis. The results will be included in Table E.2b (Appendix 2).

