Table E.4d1 Summary of the Risk Perception (PRI-P CC) Questionnaire by visit. <Question 1 of 18>  
Population: <Per-Protocol/Intention-To-Treat>

<Question>

Visit	Score	Group HnB	Group EC
Visit 4	1	XX (XX.X%)	XX (XX.X)
	2	XX (XX.X%)	XX (XX.X)
	3	XX (XX.X%)	XX (XX.X)
	4	XX (XX.X%)	XX (XX.X)
	5	XX (XX.X%)	XX (XX.X)
	6	XX (XX.X%)	XX (XX.X)
Visit 5	1	XX (XX.X%)	XX (XX.X)
	2	XX (XX.X%)	XX (XX.X)
	3	XX (XX.X%)	XX (XX.X)
	4	XX (XX.X%)	XX (XX.X)
	5	XX (XX.X%)	XX (XX.X)
	6	XX (XX.X%)	XX (XX.X)
Visit 6	1	XX (XX.X%)	XX (XX.X)
	2	XX (XX.X%)	XX (XX.X)
	3	XX (XX.X%)	XX (XX.X)
	4	XX (XX.X%)	XX (XX.X)
	5	XX (XX.X%)	XX (XX.X)
	6	XX (XX.X%)	XX (XX.X)
Visit 7	1	XX (XX.X%)	XX (XX.X)
	2	XX (XX.X%)	XX (XX.X)
	3	XX (XX.X%)	XX (XX.X)
	4	XX (XX.X%)	XX (XX.X)
	5	XX (XX.X%)	XX (XX.X)
	6	XX (XX.X%)	XX (XX.X)

<File: [..]\Work\_In\_Progress\[..]\Statistica\Programmi\xxxxx.sas>

<Source: [..]\Work\_In\_Progress\[..]\Gestione Dati\Dati SAS\xxxxx.satd7sas> Generated on XXXXXXXXXX XX:XX

Legend: 1. Nessun rischio ; 2. Rischio basso ; 3. Rischio moderato ; 4. Rischio alto ; 5. Rischio molto alto ; 6. Non so

For further information see Listing X.X

Sponsor: Center for Tobacco Research, Cessation and Prevention, [name]  
Protocol: Progetto e-cig vs IQOS

Table E.4d2 Risk Perception (PRI-P CC) Questionnaire. Inferential analysis on the mean changes at final visit from baseline

		Group HnB N=XXXX	Group EC N=XXXX	p-value
Question 1	Mean	XX.X	XX.X	X.XXXX
Question 2	Mean	XX.X	XX.X	X.XXXX
...	Mean	XX.X	XX.X	X.XXXX
Question 18	Mean	XX.X	XX.X	X.XXXX
TOTAL	Mean	XX.X	XX.X	X.XXXX

---

<File: [..]\Work\_In\_Progress\[..]\Statistica\Programmi\xxxxx.sas>  
<Source: [..]\Work\_In\_Progress\[..]\Gestione Dati\Dati SAS\xxxxx.sas7bdat>      Generated on XXXXXXXXXX XX:XX  
For the inferential analysis, the scores were considered as numbers. Score 6 was not included.  
The p-value was derived from the XXXX test  
For further information see Listing X.X

Sponsor: Center for Tobacco Research, Cessation and Prevention, [name]  
Protocol: Progetto e-cig vs IQOS

Table E.4e1 Summary of the Risk Perception (PRI-P RRP) Questionnaire by visit. <Question 1 of 18>  
Population: <Per-Protocol/Intention-To-Treat>

<Question>

Visit	Score	Group HnB	Group EC
Visit 4	1	XX (XX.X%)	XX (XX.X)
	2	XX (XX.X%)	XX (XX.X)
	3	XX (XX.X%)	XX (XX.X)
	4	XX (XX.X%)	XX (XX.X)
	5	XX (XX.X%)	XX (XX.X)
	6	XX (XX.X%)	XX (XX.X)
Visit 5	1	XX (XX.X%)	XX (XX.X)

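### The SAP calls its analysis descriptive but prints 66 unadjusted secondary between-arm p-values per population (about 77 with its text), 57 of them on questionnaires, without the between-arm difference and its interval

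*SAP*

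**What the plan says.** SAP 5 opens with "According to the study protocol the statistical analysis will be descriptive in nature". The protocol's Statistics section is narrower. It speaks of a descriptive analysis for the urinary metabolites at week 4 and of descriptive statistics for adverse events. It sets a non-inferiority threshold for the primary endpoint, and its safety paragraph itself mentions parametric and non-parametric between-group tests. The protocol's secondary objectives are worded as comparisons of the two products.

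SAP 5.1 allows for inferential analyses, and SAP 7 specifies them:

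- For smoking reduction, 7.2.1 says "The comparison between the two groups will be performed at each visit with the chi-square test".
- Adherence (7.2.2) gets a chi-square test.
- The five questionnaires (7.2.3 to 7.2.7), eCO (7.3) and EQ-5D (7.4) get a t-test or its non-parametric counterpart on change from baseline.
- Step-test changes (7.5) are to be tested item by item.

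SAP 7 adds: "The analyses of the primary and secondary endpoints will be carried out of both the ITT and PP populations".

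The shells carry this through. One is titled "Table E.4d2 Risk Perception (PRI-P CC) Questionnaire. Inferential analysis on the mean changes at final visit from baseline" and has a p-value cell for each of 18 questions and for a total. Neither document gives a testing order, a multiplicity adjustment, a key secondary endpoint, a significance level for secondary tests or an exploratory label.

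Shell E.1b (primary) prints the between-arm difference with 95% limits. E.2a, E.2b and E.3 print per-arm rates with intervals and a p-value. E.4a2 to E.4e2 print per-arm means and a p-value.

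**The concern.** Two errors of reading are at stake. First, a long column of unadjusted item-level p-values will tend to contain some below 0.05 by chance, and nothing in the plan tells the reader to discount them. The protocol's publication section commits to a separate paper comparing the products on satisfaction, craving, preferences and risk perception, and these tables would feed it. Repeating everything in ITT and PP gives a second opportunity to pick a result from largely the same people.

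Second, a p-value above 0.05 with no between-arm difference beside it invites the conclusion that the products do not differ. In a trial framed around non-inferiority that is an easy mistake, and the table would not show how large a difference remains compatible with the data.

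**Working it through.** **The plan's own figure.** SAP 3 gives "asymptotic normal distribution, upper one-tailed", alpha 0.05, "nominal power 0.80", "Ref Proportion 0.25" and "Null Proportion Diff. -0.15". Assuming a true difference of zero, which the documents do not state, the Farrington-Manning restricted estimates are 0.189 and 0.339. Then s0 = √(0.189×0.811 + 0.339×0.661) = 0.614 and s1 = √(2×0.25×0.75) = 0.612. The sample size is n = [(1.645×0.614 + 0.842×0.612)/0.15]² = 103.5, rounded up to 104 per group, as stated. This calculation covers one primary comparison only. The documents give no error rate for anything else.

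**Counting p-value cells in the shells, per population (SAP Appendix 2).**

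| Shell | Content | p-values |
|---|---|---|
| E.2a | reducers, week 12 | 1 |
| E.2b | Russell Standard rows | 5 |
| E.3 | adherence | 1 |
| E.4a2 | mCEQ: 5 domains + total | 6 |
| E.4b2 | Cue Appeal: 8 items + total | 9 |
| E.4c2 | ITUQ: 3 items + total | 4 |
| E.4d2 | PRI-P CC: 18 items + total | 19 |
| E.4e2 | PRI-P RRP: 18 items + total | 19 |
| E.5 | eCO | 1 |
| E.7b | VO2MAX | 1 |

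The total is 66 secondary, or 67 with the primary in E.1b. Questionnaires: 6+9+4+19+19 = 57, made up of 8+3+18+18 = 47 single items, 5 mCEQ domains and 5 totals.

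**Adding tests that appear only in the text.** 7.2.1 tests reducers at each visit (Visits 2 to 7, six tests, so five more than the shell). 7.4 tests EQ-5D (five dimensions and the visual scale, six tests), although shell E.6 has no p-value. 66+5+6 = 77. If 7.5 is read literally, the step test gives 7×2+2 = 16 tests, 15 more than E.7b: 77+15 = 92.

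**Expected false positives.** The significance level is an assumption: two-sided 0.05, all nulls true. The expected number is 0.05k, whatever the correlation: 57 gives 2.85, 66 gives 3.30, 77 gives 3.85.

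**Chance of at least one.** If independent, 1 − 0.95^k: 94.6% for 57, 96.6% for 66, 98.1% for 77. The 57 are not independent. Simulation with 100,000 runs per setting gives:

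| Correlation | Within scale only | Common to all 57 |
|---|---|---|
| 0.3 | 89% | 84% |
| 0.5 | 81% | 65% |
| 0.7 | 68% | 42% |
| 0.9 | 48% | 20% |

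The first column has five mutually independent scales, each with equal correlation among its items (domains for mCEQ) and a total formed from them. The documents give no correlations, so both columns are ranges, not estimates.

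**Sensitivity of the count.** The protocol's objectives and SAP 2.2 name three of the eight Cue Appeal items, while the visit schedule and shells use eight. With three, the 57 becomes 52 and the expectation 2.60.

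**Can the tests be run?** The visit schedule and SAP Appendix 4 first give these five questionnaires at Visit 4. There is no Visit 1 value, so the planned test of change from baseline needs a reference visit before any of the 57 can be computed.

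**The case against.** Several points on the other side stand. The primary is a single prespecified test, and nothing here inflates it. The SAP claims no familywise control over secondary endpoints, so a one-line statement that their p-values are nominal would answer much of the concern. Per-arm intervals are printed in E.2a, E.2b, E.3 and E.4a1, and a reader could rebuild a risk difference from the rates and arm sizes. SAP 2.2 and shell E.2a already fix week 12 for reduction. One E.2b row is loss to follow-up, which is attrition rather than a product effect. ITT (217) and PP (193) overlap heavily, so the repeat is not a second independent set of tests.

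Some stronger readings are tempting but unsupported:

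- A reader might infer that the shells alone print 77 p-values. They print 66; the rest come from the text.
- A reader might infer that every questionnaire is tested item by item. The mCEQ is tested by domain and total.
- A reader might infer that a false acceptability finding is all but certain. That needs independence, which cannot hold when totals sit beside their own items.
- A reader might judge a non-significant reduction result against the 15-point margin. That margin is set for quit rates only, and the documents assume no reducer rates from which to compute power.
- A reader might conclude that the remedy is simply to obey SAP 5. That sentence itself misattributes a general descriptive label to the protocol.

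What remains is that a nominal label alone would leave the comparison tables without the quantity that the secondary objectives ask for.

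**Conclusion.** The point holds as a worthwhile, inexpensive improvement, not as a threat to the primary conclusion. SAP 5 and SAP 7.2 to 7.5 disagree about whether the secondary analysis is inferential. The chance of at least one false positive among the 57 questionnaire tests could plausibly lie anywhere from about 42% to 95% over correlations of 0 to 0.7, and lower at stronger correlation. These figures rest on an assumed two-sided 0.05, no true differences and eight Cue Appeal items. The missing between-arm difference does not depend on any of those assumptions: it affects E.2a, E.2b, E.3 and E.4a2 to E.4e2, which hold 1+5+1+57 = 64 of the 66 secondary p-values in the shells.

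**What to change.** 1. **E.4a2 to E.4e2:** replace the item-level p-values with the between-arm difference and 95% CI for one score per scale, or per domain for mCEQ. That is 5 domains plus 4 scale scores, so 9 comparisons instead of 57 (9×0.05 = 0.45 expected false positives if the intervals are read as tests). Use the week-12 level, since there is no baseline. Keep items as frequencies in E.4b1 to E.4e1.
2. **E.2a, E.2b (quit rows) and E.3:** print the risk difference with 95% CI.
3. **7.2.1:** reconcile with SAP 2.2 and shell E.2a so that week 12 is the tested visit for reduction and other visits are descriptive.
4. **SAP 5:** correct the sentence so that it does not attribute a wholly descriptive analysis to the protocol, and state that secondary p-values are nominal and unadjusted.
5. **Before scoring:** settle whether Cue Appeal has three or eight items, and state how the totals treat the don't-know answers that the PRI-P shells leave out.

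The cost is SAP wording and minor shell reprogramming. No new data are needed. The downside is fewer p-values to quote.

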### **5.1 Premature discontinuation and missing data managing**

Patients with missing values will not be excluded from the analysis, their data will not be replaced; frequency of missing data will be given for all analyzed variables. For possible inferential analyses, the LOCF (Last Observation Carried Forward) will be adopted.

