**Follow-up Visit (V7):** Week 24 from V1 (with a tolerance of +/- 7 days): After 3 months from V6, a follow-up visit will be performed to assess the product usage and tolerability, medical/smoking/vaping/NGP behaviour, vital signs and weight/height measurement, step test, smoking abstinence/reduction assessment, quality of life perception assessment, acceptability assessment. It is remarked that the product free provision is stopped at V6.

Safety assessment (adverse and serious adverse events) and product reliability (eventual malfunctioning) will be monitored throughout the whole study and recorded in the eCFR.

**\*Remark:** At Baseline, during a period from 30 minutes to 2 hours, subjects will use and familiarize with their allocated product, as per randomization. In the same period, they will have the option to try and choose the preferred flavor of either e-liquid or heatstick, depending on the allocated arm. The choice must be maintained and cannot be changed for the 12-weeks study.

The subjects will be appropriately trained and counseled on the products, at baseline and during the whole study. Oral explanation, practical demonstration, brochures and direct help line with the investigators will be used for this objective. As specified in the exclusion criteria, the subjects will be alerted that, apart from using their allocated product and their own brand conventional cigarettes as they wish, they cannot use any other tobacco products during the 12-weeks study.

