## 9.7 Decision taken during the DRM

As described in the Minute included in Appendix 5, on the 10th June 2020 the Data Review Meeting of the study was held in call conference manner. All the decision taken were reported in the Minute. The main decision regarded the analysis population definition. All the protocol violations were evaluated, therefore the following populations were approved by the team:

Population **Safety**: 220

	e-CIG VS. IQOS Statistical Analysis Plan Version 2.0	Doc code: BIOSTAT.SAP.02
		Pag. 21 of 115

Population **Intention-To-Treat**: 217

Population **Per-Protocol**: 193

Population **Per-Protocol V7**: 177

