#### **2.4 Scelta del metodo di replicazione dei valori mancanti**

Per l'analisi inferenziale degli endpoint a risposta, il soggetto drop-out è per definizione un "non Responder" (non quitter/failure). Per gli altri endpoint, come riportato nel Capitolo 5.1 del SAP, il metodo di replicazione dei dati mancanti sarà il LOCF (Last Observation Carried Forward).

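### LOCF for the non-response efficacy endpoints carries free-supply values to an unnamed final visit, and a missed visit on the smoking endpoints has no failure rule

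*SAP*

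**What the plan says.** **General rule.** SAP Section 5.1 says of subjects with missing values that "their data will not be replaced". It then adds: "For possible inferential analyses, the LOCF (Last Observation Carried Forward) will be adopted". No endpoint is excepted.

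**Quit rate.** SAP Section 5 repeats the protocol's rule: "subjects known to have failed will be considered as treatment failures in the primary analysis along with subjects lost to follow-up".

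**DRM minute, Section 2.4 (SAP Appendix 5, in Italian).** For response endpoints it says "Per l'analisi inferenziale degli endpoint a risposta, il soggetto drop-out è per definizione un" non-responder, that is, a non-quitter or failure. For the other endpoints, citing Section 5.1, "il metodo di replicazione dei dati mancanti sarà il LOCF". SAP Section 9.7 refers to the minute for all decisions taken. Section 2.5 of the minute asked for no change to the existing text, so Section 5.1 still has its unqualified sentence.

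**Visit tested.** SAP Sections 7.2.3 to 7.2.7 and 7.4 test the change at the final visit, and Section 7.3 (eCO) the change to the last visit. Section 7.5 (step test) names no visit for its inferential analysis.

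**Supply.** The protocol's description of the follow-up visit notes: "It is remarked that the product free provision is stopped at V6".

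**Safety.** SAP Section 8 applies no replacement, so LOCF concerns efficacy only.

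**The concern.** LOCF assumes that a subject who left kept the last recorded value unchanged. In this trial every visit before Visit 7 falls in the free-supply period. If week 24 is tested, every carried value was therefore measured under conditions that no longer applied at week 24. The carried value then enters a t-test as if it had been observed, so the uncertainty about it is ignored. If subjects leave the two arms at different rates, or relapse differently after leaving, the between-arm difference is biased, in a direction that cannot be known in advance.

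The second issue is narrower. The failure rule for smoking endpoints is written for drop-outs and subjects lost to follow-up. Someone who attends Visits 4 and 6 but misses Visit 5 is neither. The only written inferential rule for that gap is Section 5.1. It would copy zero cigarettes from Visit 4 into Visit 5 and could complete the Visit 4 to Visit 6 definition of a Continuous Quitter in SAP Section 7.1.

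**Working it through.** **1. The plan's own figure.** The sample size is not in dispute and reproduces. The inputs are a rate of 0.25 in both arms (a true difference of zero is implied), margin 0.15, one-sided alpha 0.05 and power 0.80. The Farrington-Manning null rates are 0.189 and 0.339.
- Null SD: √(0.189×0.811 + 0.339×0.661) = 0.614. Alternative SD: √(2×0.25×0.75) = 0.612.
- n = [(1.645×0.614 + 0.842×0.612)/0.15]² ≈ 103.5, so 104 per group, as stated.

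**2. Which visit is tested?**
- Mock tables E.4a1, E.5, E.6 and E.7a fill the change columns only in the Visit 7 or Follow-up row. E.7a heads those columns as the change from Visit 1 to Visit 7. This points to week 24.
- Table E.1b uses *final visit* for the primary endpoint, which the protocol fixes at week 12. SAP Sections 7.2.3, 7.3 and 7.4 also promise changes at all subsequent visits. This points away from week 24 as the only reading.
- The tested visit is therefore undefined, and both cases need counting.

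**3. How many values would be carried?** SAP Section 9.7 gives ITT 217 and Per-Protocol (PP) 193, and "Population Per-Protocol V7: 177".
- PP but not PP V7: 193 − 177 = 16. They completed Visit 6 but not Visit 7.
- ITT but not PP: 217 − 193 = 24. Some or all lack Visit 6.
- Visit 7 tested, ITT: from 16/217 = 7.4% to (16 + 24)/217 = 40/217 = 18.4%.
- Visit 6 tested, ITT: at most 24/217 = 11.1%.
- Visit 7 tested, PP: 16/193 = 8.3%.

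The upper limits may be too high, because PP may also exclude violators who attended the later visits. The counts treat a completed visit as a complete record. Counts by arm are not available.

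**4. How far are values carried?** The protocol's visit schedule has the step test at Visits 1, 4, 6 and 7 only. A subject who leaves after Visit 4 has a week-4 value carried 8 weeks to Visit 6 or 20 weeks to Visit 7. EQ-5D is first repeated at Visit 4. An ITT subject seen only at Visit 2 therefore has no later EQ-5D or step test, and the SAP does not say whether the baseline value is then carried.

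**5. From counts to bias.** Let f be the share of an arm with a carried value, and d the mean gap between the carried value and what would have been observed. The arm mean is off by f×d, and the between-arm difference by f₁d₁ − f₂d₂. This is zero if f and d are equal in the two arms. The documents give neither quantity by arm.

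**6. Smoking endpoints.**

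| Situation | Rule that applies |
|---|---|
| Drop-out or lost to follow-up, quit rate | Failure (protocol, SAP Section 5, DRM minute 2.4) |
| Drop-out, reduction, read as a response endpoint | Failure (DRM minute 2.4) |
| One missed visit, subject stays, PP set | Cannot arise through Visit 6: PP completed all visits |
| One missed visit, subject stays, ITT set | No failure rule; Section 5.1 LOCF is the only text |

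**7. Why the rule matters for the primary test.** Assume 110 per arm, 22 HnB and 27 EC quitters under the failure rule, and 24 drop-outs, half of them last seen as quitters. The one-sided Farrington-Manning p-value under the failure rule is 0.032. If LOCF were used instead:
- drop-outs split 12/12 (HnB/EC): 28 v 33 quitters, p = 0.041;
- split 8/16: 26 v 35, p = 0.127;
- split 16/8: 30 v 31, p = 0.010.

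These figures show only what is at stake. DRM minute 2.4 rules LOCF out for drop-outs in this test.

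**The case against.** **A contradiction with the failure rule.** A reader who sees only Section 5.1 might infer that LOCF overrides the failure rule for quitting. The documents do not support that: Section 5, the protocol and DRM minute 2.4 all make drop-outs failures. Nor does Section 5.1 clearly contradict itself, since it can be read as leaving descriptive data unreplaced and using LOCF for inference. What stands is that the English section was left unqualified and the controlling rule sits in an Italian appendix.

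**Week 24 as fact.** It is tempting to say that the tests are at Visit 7. That is an inference from the mock-table layout; only E.7a names Visit 7 alone in its change heading, and that table is descriptive. If Visit 6 is meant, the off-supply argument falls away and only ordinary LOCF within the supply period remains.

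**A bias in ppm.** One might multiply 18.4% by an assumed eCO fall of 10 ppm and report 1.8 ppm. Over the full range of counts the result is 0.7 to 1.8 ppm, and it is an error in one arm's mean under full return to baseline. Equal errors cancel between arms. A difference of 10 points in loss would give 0.10 × 10 = 1 ppm, but neither input is in the documents.

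**Mitigation.** Efficacy is analysed in both ITT and PP, and PP needs little or no carrying through Visit 6. This stands in part. PP selects on completion, so it does not repair the ITT test. A PP V7 set exists, but SAP Section 7 assigns no analysis to it.

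**Missed visits are hypothetical.** The documents available here report none, and the footnotes to E.1a and E.1b tie the Continuous Quitter definition to PP. Section 7.1 itself has no such limit, and Section 7 applies the endpoints to ITT as well. The gap is real in wording, but its frequency is unknown.

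**Conclusion.** The point holds in a limited form and is worth correcting; it does not threaten the primary test as far as drop-outs are concerned. As written, the plan tests eCO, EQ-5D, step test and the questionnaires on singly imputed data at a visit it does not clearly name. If that visit is week 24, about 16 to 40 of 217 ITT subjects (7.4% to 18.4%) supply a free-supply value as an off-supply result. If it is week 12, at most 24 of 217 (11.1%) supply an earlier one. This assumes that PP means completion through Visit 6 and that PP subjects outside PP V7 lack Visit 7. Bias between arms requires loss or relapse to differ by arm, and its size cannot be derived from the documents. For quitting and reduction, the only opening is an intermittently missed visit in the ITT set, and the number of such visits is not given.

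**What to change.** 1. **Section 5.1, continuous endpoints.** Replace LOCF for eCO, EQ-5D VAS and step test/VO2MAX with a mixed model for repeated measures on all observed visits (arm, visit, arm × visit, baseline). Take the week-12 contrast as the main result and report week 24 separately. Keep LOCF at most as a sensitivity analysis. Analyse the remaining questionnaires and the EQ-5D dimensions on observed data.
2. **Section 5.1, smoking endpoints.** Copy the rule from DRM minute 2.4 into the English text. Extend it so that any missing smoking status needed for a quit or reduction endpoint counts as failure, whether from a missed visit or from drop-out.
3. **Sections 7.2.3 to 7.5 and the mock tables.** Name the tested visit for each endpoint.

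The cost is SAP wording and slightly more programming with standard SAS mixed-model code. No new data are needed, and the sample size stays at 104 per group. The mixed model assumes data missing at random, so it does not fully answer relapse that earlier visits do not predict; that is a smaller drawback than treating carried values as observed. The minute foresaw unfreezing and refreezing the database after its approval, so these changes could have been made before the second freeze.
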